5. TRIAL PROCEDURES

Following completion of the baseline measures, individual participant randomisation will take place. Participants will be randomised to either the intervention group to receive SNMES alongside their usual care or to the control group to receive usual care alone. Participants in both groups will continue to receive their usual care and both will take part in study assessments.

Intervention group

SNMES treatment will be started within two weeks of stroke, and within 4 days of randomisation, to account for randomisation on a Friday and starting the intervention the following week. SNMES will be targeting only the weakened stroke-affected leg muscles of the thigh (hamstring, quadriceps, triceps surae) and calf (anterior tibialis, gastroc soleus). The SNMES intervention will be delivered alongside and in addition to usual care.

Treatment with SNMES is provided using a commercial constant current 2-channel battery operated electrical stimulation device and is designed in line with previous evience. ¹³

Participants receiving SNMES will be provided with

- SNMES stimulator unit
- Knee immobiliser brace
- Ankle foot orthosis

STIM-STROKE Protocol v1.0 30-04-2025

IRAS ID: 332116 Page **24** of **70**

- 4 large electrode pads
- 4 small electrode pads
- An extra 9 volt battery
- SNMES diary (in the format of their choice, written or digital)

The treating clinician will teach the participant and their family/caregivers how to use the knee and ankle braces, apply the electrodes, set up the stimulator, carry out stimulation, remove the electrode pads, and storage of the electrode pads and stimulation devices. Participants and caregivers will be provided with an instructional booklet containing written information and videos about how to use the electrical stimulation unit, electrodes, trouble shooting, and when to stop electrical stimulation. Participants and caregivers will also be provided with a diary to track their stimulation sessions and reasons for not doing a session.

The general procedure that will be used on each muscle/joint is described below.

[figure not shown]
- 1. The motor points for the appropriate muscle will be identified by the therapist. The therapist will mark this spot on the skin with a permanent marker for future sessions. This will help to ensure consistent stimulation.
- 2. The gel electrode is placed on the muscle motor point of the weak leg (stroke affected leg). Please see the images below.

STIM-STROKE Protocol v1.0 30-04-2025

[figure not shown]
IRAS ID: 332116 Page **25** of **70**

This picture demonstrates electrode placement on the muscles of the thigh. The picture on the left is the anterior thigh muscles (quadriceps) and the picture on the right is the posterior leg muscles the hamstrings.

This picture demonstrates electrode placement on the muscles of the calf. The picture on the left is the anterior thigh muscles, the anterior tibialis and the picture on the right is the posterior leg muscles the gastrocnemius and soleus.

- 3. The stimulator leads are connected to electrodes.
- 4. For participants using the braces, the limb is positioned into a standard lower limb (thigh and calf) brace/splint and ankle foot orthosis (AFO) in a comfortable position. This is to prevent limb movement during the stimulation. Use of the brace will be optional, depending on patient preference and achieving a good limb position.
- 5. The stimulator is turned on and programmed at the following settings:
 - a. Frequency of 50Hz
 - b. Pulse duration: 450 µs
 - c. ON:OFF time: 5:10 seconds

STIM-STROKE Protocol v1.0 30-04-2025

IRAS ID: 332116 Page **26** of **70**

- d. Intensity is increased until a visible muscle contraction (this is when you can see the muscle move and contract) is produced of the muscle of interest. The intensity is then increased to participant tolerance. The intensity is determined at each individual session.
- 6. Each muscle will be stimulated for 45 contractions, this is around 30 minutes in total for all four leg muscles (12 minutes for the thigh, 12 minutes for the calf, and 6 minutes for attaching the stimulator to the electrodes and for programming the session).
- 7. When the stimulation is complete the stimulator leads are removed from the electrodes.
- 8. The electrodes are removed from the skin and stored in their packaging for the next session.
- 9. The stimulator and electrode leads are stored in the stimulator box until the next session

This process is repeated for each muscle group (quads/hamstring, gastroc soleus/anterior tibilais).

SNMES will be carried out three times a week for 12 weeks.

Participants will use the SNMES to create a co-contraction of the anterior and posterior muscles, the muscles at the front and back of the thigh as well as the front and back of the cal. For example, the quadriceps and hamstrings will be stimulated together, and the gastrocnemius, soleus, and anterior tibialis will be stimulated together. This will reduce the treatment time and participant burden. Some participants may find it more comfortable to use without the knee or ankle brace which will make it easier for caregivers to support when the participant is discharged. Some participants may experience incontinence due to their stroke or co-morbidities, not needing to use a knee brace would help with hygiene. Participants will be offered a knee and ankle brace to use if they wish. The research team will collect data around the use of the knee and ankle brace to inform a future trial.

As this is a feasibility and pragmatic trial is it useful to collect data of how participants used the electrical stimulation and braces, what was helpful and what was a hinderance.

Participants will use the SNMES while laying or semi-laying in bed. Position during use of the SNMES will be collected and used to inform a future trial.

The SNMES treatment will be integrated into the rehabilitation of the patient after stroke.

Training and Education on how to use SNMES

The Project Manager or another member of the research team with expertise in electrical stimulation will provide in-person education and training to the therapy (physiotherapists, occupational therapists, and therapy assistants) and nursing teams (including health care assistants) who will be supporting the participants to carry out the SNMES protocol. The education and training will encompass:

- how to use the stimulation unit setting up the stimulator unit, carrying out the stimulation, turning off the stimulator unit
- electrode placement (finding the motor point on the muscle)
- putting on and taking off the leg brace and AFO
- electrode and stimulator unit storage
- technical support/trouble shooting.

STIM-STROKE Protocol v1.0 30-04-2025

IRAS ID: 332116 Page **27** of **70**

Following the training, the NHS staff will help to facilitate the SNMES intervention. Following the training session, the NHS staff will complete a competency sign off with the project manager or local trust PI to ensure the team are using the stimulation in line with the protocol. The Project Manager and research team will be available for support and questions, as needed.

Education (written and video/audio formats) on SNMES use, putting on/taking off the leg brace, applying the electrodes, connecting the stimulator lead wires, expectations of SNMES, how to use the stimulation, tips for managing common problems, and technical support will be privided to both the participants with stroke, their family/caregivers, as well as to the health care staff on the stroke ward supporting the intervention. The research team contact details will be provided to the therapy teams, participant, their family and significant others supporting them.

Participants in the SNMES intervention group will have an initial treatment session with a qualified therapist who will locate the correct electrode placement for the individual mark this with a skin marker for future sessions. The mark will be updated as needed if it fades. The therapist will educate the patient on the SNMES, troubleshooting, and SNMES current parameters. Following the initial treatment, clinical staff on the ward (including healthcare assistants, nursing staff, and rehabilitation staff band 3 and above) will assist the participant to use the SNMES device 3 times a week for 12 weeks as described above. During this time the therapists will continue to show the patient and their carers how to apply the electrodes and switch on the device to the pre-determined treatment setting so that the patient and family can self-manage the treatment upon discharge where possible. When the participant or their caregiver/family can apply the SNMES on their own they will be able to initiate the treatment sessions independently.

Once set up, SNMES is self-administered and does not require health care staff supervision. Set up and removal of the SNMES stimulators and brace will take around 5-10 minutes for the health care professional, family member, or participant.

When participants are discharged from the hospital, the stimulator and leg braces will go with them to continue the intervention at home, in rehabilitation, or in a care home. The research assistant will work closely with the rehabilitation teams to track where participants are discharged for seamless continuation with the SNMES protocol, data collection, and return of the stimulator when the intervention is complete. If the participant is discharged to a care home or further rehabilitation, or community rehabilitation, the Project Manager or another member of the research team on the delegation log will orient the respective rehabilitation team to the research study. If the team is outside the trust in which the research is taking place, the staff at the care home or other community teams will also complete the skills competency after training and be added to the delegation log. SNMES protocol, and how to do the SNMES intervention (how to position the electrodes, put on and take off the brace, use the stimulator and seek technical support/trouble shooting). This will help to ensure the intervention can continue after discharge from the hospital.

We will ask participants/caregivers to maintain a treatment diary to track treatment sessions. Participants will log when and where they completed an SNMES session, how they felt during the sessions, any barriers or facilitators to the sessions, and reasons for not completing a session. The treatment diary will be available either in a paper or online format participants' preference, having these options was supported by our PPI work. This will help the team to identify what diary format(s) to use in the definitive trial. Furthermore, the number and duration of sessions recorded in the diary will be cross-checked with data logged by the stimulator.

STIM-STROKE Protocol v1.0 30-04-2025

IRAS ID: 332116 Page **28** of **70**

Control Group

Participants in the control group will continue to receive their usual care. Control group participants will take part in all study assessments. A subgroup of 8 participants from the control group will be invited to take part in an interview at the end of the intervention period to explore their experience of taking part in the study.

All participants will complete follow up assessments at 6-weeks (Visit 2), 12-weeks (Visit 3) and 6 months (Visit 4) after randomisation. These assessments will be administered by research practitioners and take place at the trust in which the participant was admitted for their stroke (UDH or the second site). If the participant is not able to walk or completes transfers by hoist the assessment can be carried out in the community at their place of residence. Research team members that undertake assessments in the participant's place of residence and will follow lone working policies associated with the trust.

Follow up Assessments

A summary of the study baseline and follow up assessments are in Section 5.5 and 5.6 as well as in Table 2 in Section 5.6.

5.1. Participant Identification, Screening, and Recruitment

Participants with stroke

The recruitment strategy has been developed in collaboration with the Public Advisory Group (PAG).

Screening and recruitment will be from the acute stroke unit. Eligible participants will be identified through screening of all new and current stroke admissions to the trust. Screening will be completed by a research practitioner (RP); e.g. (but not limited to) research nurse (RN), or research physiotherapist (RPT) as well as clinicians working on the stroke units. The RP will screen new admissions of people with stroke against the eligibility criteria as well as attend ward rounds to facilitate identification of patients that meet the screening/eligibility criteria. Clinical teams that identify someone that meets the eligibility criteria will notify the research team and research practitioners. At both sites, either clinicians in the therapy team or research staff involved in screening are employed by the participating site's R&D team (e.g. research nurses or research physios) routinely have access to patient data as part of their role.

When a RP identifies a patient with stroke who meets the eligibility criteria, they will provide the patient with the participant information sheet. If it is unclear from the chart or ward rounds if the patient is eligible, the RP will refer to the treating therapist to confirm the person with stroke meets the eligibility criteria (e.g. strength and walking ability) prior to providing the participant information sheet.

A detailed screening log will be kept detailing stroke admissions, those meeting the screening eligibility criteria, those that do not meet the criteria and why (which criteria they do not meet), those approached about the study, and reasons for declining if the participant is willing to provide a reason, they do not have to.

If a patient is screened and is meets all eligibility criteria except they are not medically or neurologically stable, they will continue to remain on the screening log and checked on for

STIM-STROKE Protocol v1.0 30-04-2025

IRAS ID: 332116 Page **29** of **70**

10 days. If at 10 days the patient is medically/neurologically stable and meets all inclusion criteria they will be provided information about the study, if they do not meet the eligibility criteria then they will be excluded.

The RP will provide the patients that meet the screening criteria with a participant information sheet (PIS) about the study. The PIS will be in multiple formats to meet the needs of all people after stroke. PIS formats include, written, written easy read, and a video version. The various formats were recommended by our patient and public involvement work to meet the diverse needs of people after stroke (and their caregivers/significant others) this will provide a more equal opportunity for understanding the information and participation.

It will be explained to the potential participant that entry into the trial is entirely voluntary and that their treatment and care will not be affected by their decision. It will also be explained that they can withdraw at any time. In the event of their withdrawal, it will be explained that their data collected thus far (prior to withdrawal) cannot be erased and we will seek consent to use the data in the final analyses where appropriate.

When participants provide consent they will be providing consent to the RCT as well as to the qualitative study which are semi-structured interviews. A subgroup of participants in the SNMES group (n=12) and in the control group (n=8) will take part in a semistructured interview. The subgroup will reflect the range of functional ability in the study, to understand participant experiences.

Clinician and Health Care Professional Participants

Clinicians (therapists, nurses, health care assistants) who have supported the participants with stroke to carry out the SNMES intervention will be invited to take part in a clinician focus group discussion. They will be recruited from participating NHS sites via announcements at team meetings and research project updates in which participant information sheets will be provided to those that are interested in taking part. It will be made clear that taking part or not taking part will have no impact on their job within the NHS or their ability to continue to support the study.

Those that are interested in taking part will contact the project manager or research team and complete a form giving their permission to share their contact details with the research team to allow them to discuss the focus group discussion.

The focus group discussions will take place after the the completion of the study intervention period.

Caregiver Participants

A convenience sample of caregivers/family members who supported the participants with stroke to use the SNMES will be invited to take part. To understand a range of experiences the team will aim to purposively sample caregivers to participants with stroke with a range of functional abilities.

Caregivers will be provided with brief explanation of the interviews and study and will be given a caregiver PIS at the baseline assessment (Visit 1). Caregivers that are not present at the baseline assessment the caregiver PIS will be left for them with the person with stroke. Those that are interested will be able to contact the project manager or research

STIM-STROKE Protocol v1.0 30-04-2025

IRAS ID: 332116 Page **30** of **70**

team via phone or email to let them know of their interest. The research team will follow-up with the caregiver at Visit 2 and Visit 3 to explore their interest in the interviews if they have not been in touch with the research team.

Interested caregivers will complete a form giving their permission to share their contact details with the research team to discuss the study and potential qualitative interview.

The interviews will take place after the intervention period around Visit 3 (12-week follow-up).

[figure not shown]
It will be made clear that the team are not able to interview everyone who responds that is interested but that a subgroup of those willing to take part in an interview will be interviewed.

IRAS ID: 332116 Page **31** of **70**

. Figure 2 Caregiver Study Flow Chart

IRAS ID: 332116 Page **32** of **70**

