2.3. Outcome measures/endpoints

Feasibility and feasibility measurement

As this is a feasibility study the primary outcomes of interest relate to aspects of feasibility and acceptability. A red, amber, green (RAG) system will be used to identify if the feasibility study should progress to a definitive trial. Section 7.3 Statistical Analysis Plan specifies the RAG system in more detail. The aspects of feasibility and acceptability that will be explored are:

STIM-STROKE Protocol v1.0 30-04-2025

IRAS ID: 332116 Page **18** of **70**

- 1. Interviews with people with stroke and their caregivers as well as focus groups with clinicians to explore their experiences and views about the acceptability of the SNMES intervention. Furthermore exploring/tracking adverse events and adverse reactions to treatment with SNMES (a common side effect of electrical stimulation is skin irritation from the electrode pads) will contribute to the determining the feasibility and acceptability of the intervention.
- 2. Study enrolment rates and screening (the number of patients who agree to take part of those eligible). Where possible reasons for not taking part will be recorded to help plan the definitive trial. Additionally. data will be collected on the time duration between hospital admission and randomisation.
- 3. Through a participant diary, records within the electrical stimulation machine, and participant/caregiver interviews we will estimate engagement with the protocol and explore reasons for low or non-engagement with the protocol/not achieving recommended dose. This will help the team to identify if the suggested dose is feasible and acceptable on a larger scale.
- 4. Through participant/caregiver interviews, therapist focus groups, and completeness of collected data explore the feasibility and acceptability of the outcome measures used. Acceptability of candidate outcomes measures and their variability to inform the selection of outcomes, including the primary outcome, for a definitive trial, likely to be the 10-Metre Walk Test.
- 5. The data collected (including those from the outcome measures and participant interviews, data completeness, and standard deviation estimates) will inform the sample size considerations and primary outcome measure for the definitive trial.

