5.2.1 Patients with Stroke

Individuals that meet the inclusion criteria will be provided with verbal and written information including a PIS (described above) in the format(s) of their choice. Potential participants will be given at least 24 hours to consider if they want to take part. Patients will be encouraged to speak to their family and friends about the study and ask any questions they may have.

Individual participant informed consent will be taken for participation in the study (both the quantitative aspects and qualitative aspects). Individuals will be made aware that a subgroup of participants will be included in the qualitative study and they may or may not take part in the qualitative component.

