5.2.1.2 Process for assessing capacity

If the approaching clinician/research practitioner expresses doubt about the person's ability to provide informed consent for the study they will conduct a capacity assessment. If the

STIM-STROKE Protocol v1.0 30-04-2025

IRAS ID: 332116 Page **33** of **70**

patient meets the criteria laid out in the Mental Capacity Act, ²⁶ a capacity assessment will be completed.

The capacity assessment will be completed by a member of the clinical/research team who are trained in capacity assessment, understand the detail of the research study, and have delegated responsibility (such as a Research Practitioner or clinician) on the delegation log. The trusts will follow their local procedures for capacity assessment using their local forms and documentation to document the capacity assessment in the patient's medical notes.

Where appropriate, the person completing the capacity assessment may request assistance from a member of the clinical team, such as a Speech and Language Therapist (SLT) or Psychologist, to aid assessment. SLT will provide particular expertise to ensure that people with a language impairment as a result of their stroke are given appropriate and individualised support to understand the information that is presented to them, and to communicate their thoughts and wishes. The Easy Read PIS version, or the video PIS version will be used to support this process.

Irrespective of whether or not someone has capacity, the views expressed by the person will be given precedence when deciding whether or not to proceed. In people who are deemed to lack capacity, any views that are expressed through the facilitated conversation will be given priority when deciding whether or not to pursue a consultee declaration. For example, if the patient expresses anxiety about any part of research process, such as using electrical stimulation, then we will not proceed with seeking a consultee declaration. We will not enrol anyone in the trial who communicates that they do not wish to participate in any aspect of the study. Participants are free to withdraw from the study at any time without giving a reason. Withdrawing from the study will have no effect on their usual rehabilitation.

The process for assessing capacity is described below in Figure 3.

[figure not shown]
STIM-STROKE Protocol v1.0 30-04-2025

IRAS ID: 332116 Page **34** of **70**

Figure 3 Process for Capacity Assessment

IRAS ID: 332116 Page **35** of **70**

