Please see section 5.8 Qualitative Assessments for complete details. A brief description of the semi-structured interviews and focus group discussions are below.

Participants with stroke

A convenience sample of eight participants from the control group and 12 participants from the intervention group will be invited to take part in a semi-structured interview. The sample will be representative of the participants that took part in the study e.g. level of functional ability.

The semi-structured interview will explore the participants experience of the study, recruitment methods, randomisation, data collection, and SNMES if they were in the experimental group. The semi-structured interview will be between 30-45 minutes. People with communication difficulties will be supported to take part.

Caregivers

STIM-STROKE Protocol v1.0 30-04-2025

IRAS ID: 332116 Page **46** of **70**

A convenience sample of 10 caregivers who supported participants with stroke in the SNMES group will be invited to take part in a semi-structured interview. The sample will be representative of the participants that took part in the study e.g. level of functional ability.

The semi-structured interview will explore the caregivers experience of the study, the study methods, and supporting the person with stroke to use the SNMES. The semi-structured interview will be between 30-45 minutes.

Clinicians

A convenience sample of 10 clinicians will be invited to take part in a focus group discussion.

The focus group will explore the clinicians' experience of the study, recruitment methods, data collection, SNMES. The focus group will be between 45 minutes and 1 hour.

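### Entry consent is written as one package covering the RCT and the interviews, so a patient willing to be randomised but not interviewed may be turned away and RCT uptake can be understated

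*Protocol*

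**What the plan says.** Three places describe what a patient with stroke agrees to at entry.

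- Section 5.1: "When participants provide consent they will be providing consent to the RCT as well as to the qualitative study which are semi-structured interviews".
- Section 5.2.1: "Individual participant informed consent will be taken for participation in the study (both the quantitative aspects and qualitative aspects". The next sentence tells people that a "subgroup of participants will be included in the qualitative study and they may or may not take part in the qualitative component".
- Section 5.2.1.2 (assessing capacity) has a paragraph that opens "Irrespective of whether or not someone has capacity, the views expressed by the person will be given precedence when deciding whether or not to proceed" and later states: "We will not enrol anyone in the trial who communicates that they do not wish to participate in any aspect of the study".

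Other places use the language of invitation. Section 5 says "A subgroup of 8 participants from the control group will be invited to take part in an interview", timed at the end of the intervention period. Section 5.6 says "A convenience sample of eight participants from the control group and 12 participants from the intervention group will be invited to take part". The Trial Summary also speaks of inviting a sub-sample. Section 8.2 mentions consent to passing contact details to the university that arranges the interviews and focus groups. By contrast, Sections 5.1 and 5.8 say simply that the selected subgroup will take part.

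Section 2.3 defines enrolment uptake as "the number of patients who agree to take part of those eligible". Table 3 in Section 7.3 rates recruitment by a count against a target of 60: green from 50, amber from 30 to 49, red below 30.

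No section says how to handle or count a patient who would join the RCT but not be interviewed.

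**The concern.** The interview is a nested component needed from 20 of 60 participants (12 intervention, 8 control). The definitive trial's recruitment will depend on willingness to be randomised, treated and assessed. If agreement to a recorded interview is a condition of entry, the feasibility study measures willingness to accept the RCT and the interview together. The error then runs one way: an interview-only refuser can lower measured RCT uptake and can never raise it.

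Uptake is a primary feasibility outcome and, with SD precision, one of the two stated bases for the sample size in Section 7.1. The protocol also handles the other participant groups differently. Caregivers can decline the interview without affecting the patient's place in the study (Sections 5.2 and 5.9), and clinicians can decline the focus group without affecting their support of the study (Sections 5.1 and 5.2). There is no matching sentence for patients with stroke or for the consultee declaration.

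**Working it through.** **Step 1. Set the passages side by side.**

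- Sections 5.1 and 5.2.1 put the RCT and the interviews under one consent and describe no opt-out at that point.
- The rule in Section 5.2.1.2 stands under a heading about capacity. However, its paragraph expressly covers people with and without capacity, and the rule applies to anyone. Its wording could mean unwillingness about at least one aspect or about every aspect. The example in the same paragraph, anxiety about one part of the research process, points to the first.
- The statement in Section 5.2.1 that a person may or may not take part can describe selection by the team or choice by the participant.
- The invitations in Sections 5 and 5.6 imply that an enrolled participant may say no. They do not help someone who says no at entry.

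The literal reading therefore excludes the interview-only refuser, while other text points the other way. The protocol does not settle it.

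**Step 2. Reproduce the plan's denominator.** Section 7.2 gives 298 patients with a qualifying leg score at the sponsor's hospitals and about 50% eligible: 298 × 0.50 = 149, the number to be approached. With the target of 60, implied uptake is 60/149 = 40.3%. This treats those approached as the eligible. The 298 is one site's figure, so 149 is used only because it is the plan's own number.

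**Step 3. Effect of interview-only refusal.** Let x be the share of RCT-willing patients who refuse only the interview and are not enrolled. The documents give no value for x, so a range is assumed. Of a fixed 60 RCT-willing patients:

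recruits = 60 × (1 − x); measured uptake = 60 × (1 − x)/149

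| x (assumed) | Recruits | Measured uptake | Loss in points | Table 3 |
|---|---|---|---|---|
| 0% | 60 | 40.3% | 0 | green |
| 5% | 57 | 38.3% | 2.0 | green |
| 10% | 54 | 36.2% | 4.0 | green |
| 20% | 48 | 32.2% | 8.1 | amber |

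**Step 4. Where the rating changes.** Green needs 50 or more: 60 × (1 − x) < 50 when x > 10/60 = 16.7%. In whole patients that is 11 refusals (11/60 = 18.3%), leaving 49 recruits and uptake of 49/149 = 32.9%. This holds only if the 60 is a ceiling and no further patients are approached.

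**Step 5. Scale.** Section 7.1 plans a 10% margin of error for uptake. A loss of 2.0 to 8.1 points lies within that margin. At the upper end it is of similar size and, unlike sampling error, always goes in the same direction.

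**The case against.** The best counter-case is that entry consent means only agreeing that one may later be invited. The wording in Section 5.2.1, the invitations in Section 5, Section 5.6 and the Trial Summary, and the contact-sharing consent in Section 8.2 all fit this. The exclusion rule sits in the capacity section, concerns respect for dissent, and is not among the exclusion criteria in Section 4.2. The consent form is not in the copy reviewed, so a separate optional interview item may already exist. Reasons for declining are logged when offered (Section 5.1), which could reveal some interview-only refusals.

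Much of this stands, and it is why the point is one of reconciliation. It does not remove the problem. Staff enrol from the protocol, whose entry text describes one package. Giving a reason is voluntary, and no interview-only category is described.

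A reader might go further and infer any of three things, none of which the documents support:

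- **That uptake will be understated.** There is no refusal rate, and at zero refusals there is no bias.
- **That the study will slip from green to amber.** Table 3 scores a count. Section 7.2 has a two-month contingency and cites about 2000 admissions across both sites, so lost recruits could be replaced.
- **That the loss falls mainly on people with communication or cognitive difficulty.** Nothing shows this, and Sections 5.6 and 5.8 promise support for people with communication difficulties to be interviewed.

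**Conclusion.** The point holds as an unresolved conflict in the consent text, with a one-directional risk to a primary feasibility estimate. Taken literally, Sections 5.1, 5.2.1 and 5.2.1.2 exclude a patient who accepts the RCT but not the interview; other sections suggest that they need not. If such exclusions occur, RCT uptake can be understated. Under an assumed 5% to 20% interview-only refusal it would read 38.3% to 32.2% instead of 40.3%. The Table 3 rating is less exposed: it changes only at 11 or more refusals out of a fixed 60 that are not replaced. These figures rest on the plan's 149 as denominator and on a refusal share that the documents do not supply. The matter is modest in size but worth correcting, because compulsory interview agreement from all 60 gains little when 20 interviews are needed.

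**What to change.** 1. Reconcile Sections 5.1, 5.2.1 and 5.2.1.2 by stating that declining the interview does not bar enrolment in the RCT, and limit the rule in Section 5.2.1.2 accordingly.
2. Make the interview a separate optional item on the participant consent form and on the consultee declaration, if it is not one already. The item then records how many accept the trial but not the interview.
3. Draw the 12 intervention and 8 control interviewees from those who opt in.

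The cost is a small amendment to the protocol and, where needed, to the consent documents, with ethics review. The interview pool becomes somewhat smaller and self-selected, which should be acknowledged when the qualitative findings are reported. With 20 interviews needed from 60 participants, there is room for this.
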